Investigating the Effectiveness of an Entertainment Education Short Film for Internalized HIV

Stigma Reduction, Intimate Partner Status Disclosure Intentions, and Antiretroviral Medical

Adherence Intentions: A Randomized Controlled Trial Among Black Women Living with HIV

in the Southern U.S.

ClinicalTrials.Gov Identifier: NCT03898063

April 1, 2020

Study #: 20170967 Effective Date: 4/1/2020

IRB#: 20170967

1) **Protocol Title**

An experimental investigation of the effects of an entertainment education short film on internalized HIV-related stigma, sexual partner status disclosure and antiretroviral therapy (ART) medical adherence among Black HIV-positive women in the Southern U.S.

2) Objectives*

This investigation seeks to understand if and how, the *90 Days* film can be used as an intervention to address HIV-related stigmas, intimate partner status disclosure and HIV ART medical adherence among Black HIV positive women. HIV-related internalized stigma is unique to this population as it relates to the negative internalized attitudes possessed by an HIV positive individual (Kalichman et al., 2009). Therefore, conducting this research with HIV positive participants is paramount in understanding the impact of entertainment education on internalized stigma and status disclosure.

3) Background*

The Joint United Nations Programme on HIV/AIDS (UNAIDS; 2015) has proposed the 90-90-90 treatment target with hopes of ending the AIDS epidemic. "By 2020, 90% of all people living with HIV will know their HIV status. By 2020, 90% of all people with diagnosed HIV infection will receive sustained antiretroviral therapy (ART). By 2020, 90% of all people receiving antiretroviral therapy will have viral suppression" (UNAIDS, 2015). Within the Southern U.S., among all women, Black women account for 67% of new diagnoses (CDC, 2019). Nationally, Blacks are less likely to adhere to ART regimens and reach viral suppression. Such combination poses a local public health crisis to reaching the national goals for HIV prevention. The CDC (2017a) recommends HIV status disclosure among sexual partners as a primary preventive measure to reduce the HIV burden by increasing the likelihood of using prophylactic measures. Furthermore, HIV status disclosure has been empirically linked to increased ART adherence (Stirratt et al., 2006) another advocated HIV prevention method. Problematically, psychological inhibitions such as internalized HIV stigma, negative beliefs and devaluing of one's self due to positive HIV status, often inhibit status disclosure and medical adherence (Chaudoir & Fisher, 2010; Herek, 1999; Turan et al., 2017). In the case of HIV-positive Black women, race and gender-related stigmas make status disclosure markedly more difficult (Henkel, & Kalichman, 2008).

Considering the central role of status disclosure and medical adherence in managing the HIV epidemic, identifying effective strategies that address such inhibiting mechanisms is critical. The present proposal contributes to this literature by conducting an experimental evaluation of a short entertainment education (EE) film about HIV status disclosure and management among Black HIV positive women living in Miami. EE refers to prosocial, persuasive messaging embedded into entertainment media (Moyer-Gusé, 2008). Entertaining media can influence persuasive outcomes through a variety of cognitive and emotional mechanisms. However, one particular strength of EE is it can provide social scripts for complex social interactions like HIV status disclosure. Moyer-Gusé, Chung and

Version 10.5.2018 Page 1 of 11

Jain (2011) found participants who viewed a television program addressing HIV testing and sexual health dialogue reported higher levels of self-efficacy for engaging in these difficult conversations. Moreover, in comparison to a condition in which sexual discussion modeling was not demonstrated, participants who viewed the full episode were more likely to discuss HIV storylines with others (Moyer-Gusé, et al., 2011). In this regard, EE may provide a less threatening method for initiating sexual health discourse (Moyer-Gusé, et al., 2011). For understandable reasons, people are hesitant to disclose their HIV status. Moyer-Gusé's (2008) entertainment overcoming resistance model (EORM) provides a rationale for how EE can overcome this resistance.

4) Inclusion and Exclusion Criteria*

Participants for the manipulation check will be Black women between the ages of 18-45, clinically diagnosed with HIV/AIDS. For the main study, participants will be Black women ages 18-50, clinically diagnosed with HIV/AIDS. Women who are pregnant or think they may be pregnant will not be excluded from the study; as there is minimal risk associated with this research. No data will be collected regarding one's pregnancy or baby. In addition, the study will require participants to speak and comprehend English. Respondents will also need to have a working email address so that they can receive their compensation. Additionally, for those currently enrolled, they will need an email address to receive a study reminder for their follow up survey. Participants from the previous iteration of the 90 DAYS focus group will only be able to participate in the manipulation check. For the main study, participants from the previous 90 DAYS focus group iteration will be excluded.

5) Procedures Involved*

We propose a randomized clinical trial (RCT) with a pre and post questionnaire assessing two conditions: (1) standard-of-care brochure (control condition) and (2) the EE film (treatment condition). For those currently enrolled in the study (N=3) outcomes will be assessed with two post questionnaires, the first to assess intentions immediately after exposure to the study conditions and the second to assess lasting effects of the intervention on behavior one month later. The second questionnaire will primarily evaluate participants' disclosure attitudes and beliefs, intimate partner disclosure intentions, medical adherence intentions, disclosure behavior, adherence behavior and reported internalized stigma. However, for newly enrolled participants only one post questionnaire will be assigned. Therefore, after completing the pre-test, intervention, and immediate post-test, they will not complete a follow up questionnaire. Thus, instead of participating in two waves of data collection, newly enrolled participants will only participate in one wave of data collection.

Prior to beginning the study, researchers will conduct a manipulation check for the PSA to ensure it is yielding the intended effects. The pre-test of the PSA will be conducted with 15-30 research participants. For the manipulation check, participants will provide verbal consent in place of signed consent. Therefore, completing the pre and post-test questionnaires will serve as their agreement to study participation. Participants will either be randomly assigned to view the PSA or to the control condition in which no stimulus will be used. Study conditions will

Version 10.5.2018 Page 2 of 11

be randomly assigned based upon the dates of data collection. Participants viewing the PSA will complete a brief pre-stimulus questionnaire. Once completed, respondents will view a brief (30-60 seconds) PSA addressing key points displayed in the *90 DAYS* narrative. At the conclusion of viewing the PSA, participants will complete a brief post-test questionnaire. If assigned to the control condition, participants will only complete the brief post-test questionnaire. All participants in the manipulation check will be compensated \$25 for their participation in the manipulation check.

Traditionally, Black women within the U.S. are a hard to reach population for research involvement (Jones, Lacroix, & Porcher, 2017). Literature suggests that Black women often experience an amalgam of barriers to research engagement such as: lack of transportation, need for a babysitter, and extensive caregiving responsibilities for loved ones (Webster et al., 2018). Considering this, the National Institutes of Health is strongly encouraging researchers to identify strategies that increase study participation among this demographic (Jones, Lacroix, & Porcher, 2017). For this reason, the current study will align with peer reviewed research and conduct the experimental sessions for the main study via the online Qualtrics platform (Jones, Lacroix, & Porcher, 2017). All responses to questionnaires will be anonymous.

Due to the sensitive and hard to reach nature of this study population, multiple recruitment strategies will be implemented. Firstly, a two-step recruitment process will be employed. Based upon the inclusion and exclusion criteria, clinic staff throughout the Jackson Health System as well as other HIV service providers across the state of Florida, will inform patients of the study via print and virtual flyers, sent via email. Dependent upon the study schedule, research team members maybe stationed at recruitment sites to speak with interested patients who desire further information. If research staff are not onsite, interested participants can contact the identified study team member listed on the recruitment flyer should they have further questions. All virtual flyers will be sent by clinic staff via a restricted email server to patients who have agreed to be contacted via email by their health provider. For patients who receive a printed or virtual copy of the study flyer, if they are interested in participating, they will visit the Qualtrics link provided on the flyer. Once they are on the study site, participants will read the consent form which thoroughly outlines the study's purpose, inclusion criteria, risks, benefits, compensation, voluntariness, and researchers' contact information. Should participants decide the study is a good fit for them, they will be able asked to consent by clicking the "next" button. Upon clicking the "next" button participants will be asked screening questions based upon the study's inclusion criteria (See updated measures guide). Once screened, if participants meet the eligibility requirements they will be guided through the study. Should participants not meet the eligibility criteria, they will be redirected to the end of the study and thanked for their time. Participants will be fully aware via the consent form that they can withdraw from the study at any time.

The second recruitment method will consist of paid targeted Facebook advertising. This recruitment strategy has yielded successful results in similar populations as the

Version 10.5.2018 Page 3 of 11

current study (Jones, Lacroix, & Porcher, 2017; Mitchell & Petroll, 2012). Using data provided by the Centers for Disease Control and Prevention (CDC) and geographic information systems mapping, researchers will run Facebook advertisements in specific states, across the Southern U.S., that are identified to have moderate to increased prevalence of HIV among Blacks. In addition to using specific states, as carried out by other researchers, study investigators will set specific criteria to distinguish which Facebook users will be exposed to the ad (Jones, Lacroix, & Porcher, 2017). The inclusion criteria for the Facebook advertisements will include: Black women between the ages of 18-50 living within the Southern U.S. Similarly to those who receive the print or virtual flyer, participants recruited via Facebook will be able to click on the link in the advertisement to be redirected to the study's consent form. If they deem the study is a good fit for them, they will proceed by clicking the "next" button. Once they select "next", participants will complete the pre-test questionnaire, view one of the assigned stimuli, and complete the initial post questionnaire. Once all anonymous responses have been submitted, a randomized code will be provided to participants. Participants will be instructed to enter this randomized code along with their email address to receive compensation. Three weeks after completing the pre- and posttest questionnaire, participants will receive a reminder, via the provided email, to complete the follow up questionnaire. Similarly, to part one of the main study, once all anonymous responses are submitted, participants will receive a randomized code. They will be asked to enter the randomized code and their email address to receive their final compensation. Lastly, researchers will also request HIV servicing agencies to post the study flyer on their Facebook pages.

The third recruitment strategy consists of using a Qualtrics panel. According to Qualtrics, "A market research panel, also known as an online sample, is a group of people recruited to respond to a survey. They are typically chosen from a prearranged pool of respondents who've agreed to be contacted by a market research service in order to respond to surveys." Employing the study inclusion/exclusion criteria, Qualtrics panel, recruits willing participants for study participation. Participants recruited via the Qualtrics panel will be compensated directly via Qualtrics. They will receive a \$50 gift card for their participation.

Across all forms of recruitment, study conditions will be randomly assigned via the Qualtrics system. Once a participant provides consent and is screened for study inclusion, participants will complete the pre-test questionnaire. After completing the pre-test questionnaire, respondents will be assigned to one of two study conditions. They will either be asked to view one of the following: a brochure on safe disclosure or the 90 DAYS film. Upon completing one of the interventions, participants will be asked to immediately complete the post-test questionnaire. For participants recruited outside of the Qualtrics Panel, once all anonymous responses are submitted, they will be directed to a separate link to enter their randomized generated code and email address. The purpose of the randomized code is to verify that the participant completed the study. The purpose of the email address for those currently enrolled is two-fold. Firstly, it will allow researchers to compensate participants with a virtual \$30 Amazon gift card. Secondly, it will allow researchers to provide a follow up email, within 3-4 weeks, containing the link to the second

Version 10.5.2018 Page 4 of 11

post-test survey. Participants will be compensated with a \$20 virtual Amazon gift card. Altogether, currently enrolled respondents in the main study (N = 3), will receive a total of \$50 for their participation in the study. After each data collection, participants will be reminded of their right to withdraw their responses from the study without penalty.

For newly enrolled participants, whether recruited via Qualtrics, social-media, health agencies, or word-of-mouth, only one wave of data collection will occur. Once participants complete the pre-test, intervention, and immediate post-test, they will not be re-contacted 3-4 weeks later for a follow up post-test. Newly enrolled participants who complete one wave of data collection will also be compensated with a total of \$50 in e-gift cards; just as their counterparts who were enrolled in two waves of data collection.

For participants randomly assigned to the pamphlet only condition, an opportunity to view the short film will be available upon submitting their anonymous responses to the post test survey.

6) Data and Specimen Banking*

N/A

7) Data Management

To maintain participants' privacy, identifying information will be safely maintained in a secured password protected file that only study team members will have access to. The study will be administered using Qualtrics survey software. All quantitative data will be analyzed using SPSS 24 and Mplus.

8) Risks to Subjects

There are no physical risks anticipated with participation in this study. It is possible that participants may experience some stress in completing the questionnaire, and/or some inconvenience in the time taken to participate in the two waves of this study. A breach of confidentiality is also a potential risk, but measures will be taken to minimize that risk (please see confidentiality section below). Due to anticipating minimal risks, this study will not assess adverse effects.

9) Potential Benefits to Subjects

No direct benefit can be promised to you from being in this study.

10) Compensation

Participants in the PSA pre-test will be compensated \$25. Light refreshments or lunch will be served during PSA pre-test sessions. Currently enrolled participants in the main study will be compensated with virtual Amazon gift cards oppose to cash. Participants will receive \$30 for the first part of the main study and \$20 for the follow up questionnaire of

Version 10.5.2018 Page 5 of 11

the main study. Due to only participating in one wave of data collection, newly enrolled participants will receive one payment. However, just as those currently enrolled, newly enrolled participants will also be compensated with \$50 via gift card. Altogether, all participants in the main study (current and new) will be compensated \$50 in virtual gift cards. Participants recruited via Qualtrics will be compensated directly through Qualtrics. They will be compensated the amount agreed upon by their provider, which will be a minimum of \$50 in Tango gift cards. Participants recruited via all other strategies will be compensated via email with a total of \$50 in Amazon e-gift cards.

11) Vulnerable Populations

Minors, prisoners and those unable to consent will be excluded from the study. Pregnant women will not be excluded from the study. This study is presumed to have minimal risk. No data will be collected regarding one's pregnancy or baby.

12) Setting

Participant referrals and onsite recruitment will take place at the UM HIV Clinics at Jackson Memorial Hospital as well as other HIV service providing agencies across the Southern U.S., such as the AIDS Healthcare Foundation (AHF), Care Resource, Big Bend Cares, Neighborhood Medical Center, and Bond Community Health Center. Lastly, virtual recruitment will be conducted via Facebook and Qualtrics panel.

The PSA manipulation check will be conducted in the University of Miami's Clinical Translational Science Institute room or on the 7th Floor of the Soffer Clinical Research Center (CRB; rooms 710N or 710Q) located at [name] and the Batchelor Childrens Research Institute, [name], 2nd floor conference room.

Paper data for the PSA manipulation check will be stored at in the principle investigator's office at [name]. All electronic data and audio/video recordings will be stored on the password protected computers of research team members responsible for data analysis.

The main study will be conducted virtually, via Qualtrics software.

13) Resources Available

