Statistical Analysis Plan

Investigating the Effectiveness of an Entertainment Education Short Film for Internalized HIV

Stigma Reduction, Intimate Partner Status Disclosure Intentions, and Antiretroviral Medical

Adherence Intentions: A Randomized Controlled Trial Among Black Women Living with HIV

in the Southern U.S.

ClinicalTrials.Gov Identifier: NCT03898063

February 15, 2021

Introduction: Purpose of the Statistical Analysis Plan (SAP)

The purpose of this Statistical Analysis Plan (SAP) is to detail the study objectives, study hypotheses and research questions, as well as the primary outcome measures and data analyses.

Study Overview

This randomized controlled trial was conducted among Black women living with HIV in the Southern U.S. between the ages of 18 and 50. The study examined the efficacy of a short entertainment education (EE) narrative in comparison to a standard brochure for primarily improving the following: HIV status disclosure intentions, internalized HIV-related stigma, and antiretroviral medical adherence. Once consented, all participants completed a pre-test survey. Upon completing the pre-test, using the randomization feature in Qualtrics, participants were randomly assigned to one of two study arms: 1) EE narrative or 2) Brochure. After viewing the EE stimulus or the brochure, participants immediately completed a post-test survey. The primary aim of the study is listed below.

Aim 1. To investigate the effectiveness of an EE intervention for decreasing internalized HIV-stigma and increasing HIV status disclosure intentions and medical adherence intentions among Black women living with HIV in the Southern U.S.

The hypotheses guiding this research study included the following:

H_{1a-c}: Participants in the EE condition will report: a) lower levels of internalized stigma; b) higher levels of disclosure intentions; c) higher levels of medical adherence intentions.

Data Collection Plan

Participants will be recruited via two primary methods. Firstly, Facebook advertisements will be deployed to recruit participants who meet the inclusion criteria. Secondly, participants will be recruited via a Qualtrics panel.

Statistical Methods

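### Does the plan claim lasting effects on behaviour that only three women could show?

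*Protocol*

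**What the plan says.** Protocol section 5 (Procedures Involved) opens the follow-up provision with a restriction: "For those currently enrolled in the study (N=3) outcomes will be assessed with two post questionnaires". The second of these is "the second to assess lasting effects of the intervention on behavior one month later". Its listed content includes "medical adherence intentions, disclosure behavior, adherence behavior and reported internalized stigma", and this is the only questionnaire for which behaviour items are named. For newly enrolled women the end of section 5 says that "they will not be re-contacted 3-4 weeks later for a follow up post-test".

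The Facebook recruitment paragraph in the same section reads differently: "Three weeks after completing the pre- and posttest questionnaire, participants will receive a reminder, via the provided email, to complete the follow up questionnaire". It does not limit this to the women already enrolled. Women given the brochure are told of the film afterwards: "an opportunity to view the short film will be available upon submitting their anonymous responses to the post test survey".

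On the target of the trial, the section 1 title refers to "sexual partner status disclosure and antiretroviral therapy (ART) medical adherence among Black HIV-positive women", and section 2 (Objectives) likewise names disclosure and adherence without the word intentions. The SAP's Study Overview lists "HIV status disclosure intentions, internalized HIV-related stigma, and antiretroviral medical adherence". By contrast, the cover title on both documents, the SAP's Aim 1 and hypotheses, and the primary variables under Statistical Methods all refer to intentions to disclose and intentions to adhere, together with internalized stigma.

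**The concern.** Three things look wrong together. A purpose of measuring lasting behavioural effects is still on paper, although almost nobody is followed. Adherence itself appears as a target in the title, the objectives and the SAP overview, although the trial asks about intentions right after exposure. And the Facebook paragraph, which covers one of the SAP's two main recruitment routes, appears to promise a follow-up that other paragraphs rule out.

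If the trial were analysed and reported on those words, a shift in intentions could be presented as better adherence or more disclosure, or as an effect that lasts. If staff acted on the Facebook paragraph, a second wave would arise in which the brochure arm had already been offered the film, so the later contrast would be film against film on request.

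**Working it through.** The documents give no calculation on this point, so there is no stated figure to reproduce. The check is whether a reader following the plan would reach a claim about behaviour or duration.

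**Who is followed**
- Section 5 limits the second questionnaire to the currently enrolled, N = 3, and repeats that limit in the compensation details of the same section.
- Section 4 asks for an email address for a follow-up reminder only from those currently enrolled. Section 10 gives new participants one payment because they take part in one wave.
- Section 16 allows up to 400 women in the main study. Share with follow-up at full enrolment: 3 / 400 = 0.75%. Share without: 397 / 400 = 99.25%.
- Against this stand the Facebook sentence and smaller remnants: section 8 mentions two waves, section 17 collects contact details partly to schedule a second wave, and section 18 mentions a follow-up reminder. These are unqualified descriptions of procedure. The statements limiting follow-up are explicit and give the reason, namely that new participants have one wave instead of two.

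**What is analysed**
- The SAP's Study Overview describes a pre-test, randomisation, the film or brochure, and an immediate post-test. There is no later visit.
- Aim 1, H1a-c and the primary variables are internalized stigma, disclosure intentions and adherence intentions. No behaviour variable appears.
- The lone phrase naming adherence in the SAP overview is followed within the same section by Aim 1, which says adherence intentions. The outcome to be analysed is therefore not in doubt.

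**Whether the three follow-up forms could yield a behavioural claim under the SAP's own method**
- The planned ANCOVA has an intercept, arm and age, which is 3 parameters. With 3 women the residual degrees of freedom are 3 - 3 = 0, so the model cannot test an arm effect.
- On the immediate post-test with 400 complete records the same model has 400 - 3 = 397.
- No place in either document proposes a between-arm comparison of the three, so power for such a comparison is beside the point.

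**Whether offering the film to controls affects the main comparison**
- The offer comes after the post-test is submitted. The primary outcomes are already recorded, so the randomised comparison is untouched.

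**The case for a change.** The best case for acting is that the fix costs only words, and the words matter. The background section rests its argument on actual disclosure and adherence, and a title and objectives in those terms invite a report in the same terms. The SAP is internally inconsistent about one of its three targets. It also says nothing about the three follow-up forms, and staff reading only the Facebook paragraph could re-contact women who should not be re-contacted.

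The textual part of this stands. The Facebook sentence does conflict with the rest of section 5, and the section 1 title, the objectives and one SAP phrase lack the word intentions. What does not stand is the step from there to a wrong conclusion. The pre-specified aim, hypotheses and variables are all framed as intentions and stigma, so overstating the result would mean departing from the SAP. The SAP's overview, dated February 2021 and written in the past tense, describes one immediate post-test, so it gives no sign that a general second wave took place. What recruits were actually told cannot be judged, because the consent pages are not in the reviewed copy. As for the three forms, any analyst would list them or leave them out; no test is available to misuse.

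**Conclusion.** No change to the plan is called for. Following the documents as they stand gives an age-adjusted ANCOVA on stigma and two intention measures immediately after exposure, with conclusions framed that way by Aim 1. The apparent claim about lasting behaviour concerns 3 of up to 400 women (0.75%) and is limited to them in its own sentence.

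What remains is leftover wording: one unqualified follow-up sentence, a few mentions of a second wave, and three places that omit the word intentions. It is reasonable to tidy these if the documents are reopened, but doing so would change no analysis, estimate, sample size or result. This rests on two readings: that the explicit statements limiting follow-up govern over the unqualified Facebook sentence, and that Aim 1 and the primary variables govern over the overview phrase. Both are the natural readings of the text.

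### For open-link recruits, the consent page shows the eligibility criteria and the payment before a self-report screener, and no other check of HIV diagnosis or related sensitivity analysis is described

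*Protocol*

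**What the plan says.** Protocol section 4 sets the main-study population: "For the main study, participants will be Black women ages 18-50, clinically diagnosed with HIV/AIDS".

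Section 5, in the paragraph on clinic flyers, gives the order of pages. The consent form comes first and covers "purpose, inclusion criteria, risks, benefits, compensation, voluntariness". After clicking the next "button participants will be asked screening questions based upon the" inclusion criteria. Those who fail learn little: "they will be redirected to the end of the study and thanked for their time".

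The same order appears in the section 5 paragraph that covers every recruitment route: "Once a participant provides consent and is screened for study inclusion, participants will complete the pre-test questionnaire". On the Facebook route, "participants recruited via Facebook will be able to click on the link in the advertisement to be redirected to the study's consent form". The advertisement itself is aimed at "Black women between the ages of 18-50 living within the Southern U.S", so HIV status is not a targeting criterion. HIV service agencies are also asked to post the flyer on their own Facebook pages.

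Other relevant provisions:
- Questionnaire responses are anonymous (section 5), and contact details are stored apart from them (section 17).
- The random code given at the end serves to confirm completion, not eligibility (section 5).
- Main-study participants receive $50 (section 10).
- Enrolment is capped at 400 for the main study (section 16).
- The SAP (Data Collection Plan) names Facebook advertisements and a Qualtrics panel as its two recruitment methods.
- The SAP (Statistical Methods) compares the arms on internalized stigma, disclosure intentions and adherence intentions by ANCOVA with age. It describes no validity exclusion and no sensitivity analysis.

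**The concern.** A visitor who reaches the survey through an open link reads who qualifies and what is paid, and is then asked whether she qualifies. On these routes her own answer is the only described evidence of a clinical HIV diagnosis. Someone without HIV who wants the payment could give the qualifying answers, and nothing in the available text would detect it then or later.

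The three primary outcomes presuppose that the respondent has HIV. Answers from a person without HIV carry no information about the population the trial is meant to describe. Randomisation would spread such respondents over both arms, so the expected harm is not confounding. It is attenuation of the film-brochure difference if they react less to the film, added noise if their scores sit at a different level, and an estimate that no longer refers only to Black women living with HIV.

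**Working it through.** **1. Is the order of pages confined to one route?** No. The most detailed description is in the clinic-flyer paragraph, but the all-routes paragraph repeats consent, then screening, then pre-test, and the Facebook paragraph leads to the same consent form.

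**2. Which routes lack an upstream check?**
- Clinic flyers: clinic staff inform patients with the criteria in mind, and electronic flyers go to patients who agreed to be emailed. Exposure is lower.
- Qualtrics panel: the panel provider recruits against the criteria, although no proof of diagnosis is described. Exposure is intermediate.
- Facebook advertisements, shared posts and word of mouth: nothing precedes the screener that bears on HIV status. Exposure is greatest.

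**3. What could it cost?** The documents give no effect size, SD, alpha, power or ineligible share, so there is no figure of the plan's to reproduce. What follows is an illustration.

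Inputs: at most 400 in the main study (section 16), taken as n = 200 per arm under an assumed 1:1 allocation. Also assumed: two-sided 5% test, SD 1, true standardised effect d = 0.30, ineligible share f of the whole sample, and g, the effect in ineligible respondents as a fraction of that in eligible women. The age adjustment is ignored.

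Expected effect = d × [(1 − f) + f × g].

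Power ≈ Φ(expected effect × √(n/2) − 1.96), with √(200/2) = 10.

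Worked case, f = 20% and g = 0: expected effect 0.30 × 0.80 = 0.24; power ≈ Φ(2.40 − 1.96) = Φ(0.44) = 67.0%.

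| f | Effect, g = 0 | Power, g = 0 | Effect, g = 0.5 | Power, g = 0.5 |
|---|---|---|---|---|
| 0% | 0.30 | 85.1% | 0.30 | 85.1% |
| 10% | 0.27 | 77.0% | 0.285 | 81.3% |
| 20% | 0.24 | 67.0% | 0.27 | 77.0% |
| 30% | 0.21 | 55.6% | 0.255 | 72.2% |

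The exact t-test gives 84.9%, 76.8%, 66.8% and 55.4% for the g = 0 column. With g = 1 nothing is lost at any f.

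**4. Sensitivity to the assumptions.**
- If ineligible respondents also differ by 1 SD in mean score, the SD at f = 20% becomes √(1 + 0.2 × 0.8 × 1²) = 1.077. With g = 0, power ≈ Φ(10 × 0.24/1.077 − 1.96) = Φ(0.27), about 61%.
- If d were 0.50, f = 20% with g = 0 leaves power at Φ(4.0 − 1.96) = 97.9%, but the expected estimate still falls from 0.50 to 0.40.
- f refers to the whole sample. If half the sample came by open link (an assumption) and ineligible entry occurred only there, f = 20% would need 0.20/0.50 = 40% of those recruits to be ineligible, and f = 30% would need 60%.

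**The case against.** Consent first is a legitimate design: a woman learns the purpose, risks and payment before she is asked about HIV. Advertisements and flyers have to say who is sought, and their text is not in the documents, so the criteria may be known before any survey page opens. The underlying weakness is then unverified self-report, and the page order only adds to it. This stands, and it is why the order need not be reversed outright.

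The screening questions are in a measures guide that was not available, and part of the protocol around sections 13 to 15 was also unavailable. Decoy items, consistency checks or re-entry limits may be described there. This stands too, and the point is limited to what can be seen.

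Four stronger readings are tempting but unsupported:
- A reader might infer that the whole sample is unverified. The clinic and panel routes apply the criteria upstream.
- A reader might infer that Facebook recruits skip screening, because that paragraph goes straight from consent to pre-test. The all-routes paragraph includes screening.
- A reader might infer that a failed visitor is shown which answer failed. The protocol says only that she is redirected and thanked; the available text is silent on re-entry.
- A reader might infer that the primary comparisons are certainly diluted. That needs ineligible respondents to be present and to react less to the film. Paid respondents might instead answer in line with its evident message.

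**Conclusion.** The point holds for open-link recruits. The plan as visible leaves entry by ineligible respondents unguarded beyond self-report, shows the qualifying criteria and payment beforehand, and provides no analysis that would reveal the effect on results. Facebook is one of only two recruitment methods in the SAP, so the exposed group need not be marginal.

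Whether ineligible respondents entered, in what number, and how they reacted cannot be derived from the documents. The fall from 85% to 67% power rests on d = 0.30, 200 per arm, 20% ineligible overall and no reaction to the film; it is a scale for the risk, not an estimate. The case for action is that the safeguards are cheap and protect all three primary comparisons. It is an improvement that should be made, not a flaw that invalidates the randomised comparison.

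**What to change.** In protocol section 5:
- Keep the full consent form ahead of the pre-test and randomisation.
- Word the screener neutrally: HIV within a list of health conditions, and birth year in place of an age range.
- Block re-entry from the same browser after a failed screen.
- In the pre-test, repeat birth year and ask the year of HIV diagnosis.

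In the SAP, prespecify a sensitivity analysis of the three primary ANCOVAs that excludes respondents whose pre-randomisation answers conflict, and show the results by recruitment route as well. Using only pre-randomisation answers keeps the exclusion independent of arm.

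A brief neutral screener ahead of the full consent form is an option to settle with the IRB, since it means asking about HIV before full consent.

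The cost is a few extra survey items and one extra analysis. The SAP's Study Overview describes conduct in the past tense while its Data Collection Plan uses the future. If collection is complete, the survey changes no longer apply; run the sensitivity analysis with recruitment route and any consistency items already collected.
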